4.5.2 Specimen Use

The ChiLDREN Steering Committee has developed a policy for the approval of ancillary studies – studies that will require the use of samples in the repository. ChiLDREN investigators may propose such studies; non- ChiLDREN investigators may propose such studies only if they have a ChiLDREN investigator as a co-investigator. To be approved, these studies must relate to the specific aims of ChiLDREN, namely to study the pathogenesis and natural history of biliary atresia and neonatal hepatitis or to evaluate patterns of cellular gene and protein expression in tissue specimens and plasma by viral, genomic and proteomic techniques. Examples of studies that have been proposed by ChiLDREN investigators (but as yet none are approved) are: Screening for genetic mechanisms for pathogenesis and modifiers of biliary atresia; Study of JAG1 mutations in patients with biliary atresia; Identifying genetic determinants of biliary atresia; Studying the association of perinatal viral infection with biliary atresia and choledochal cyst; proteomic analysis of neonatal cholestasis; Identifying novel

antigens and T and B cell responses in biliary atresia; The association of HLA type and biliary atresia.

These research studies are not related to clinical care; tests performed on anonymized samples will not be reported to the parents/guardians nor included in the medical record.

The goal of the NIDDK repositories is to make samples available for investigations that have not been specified. Until the funding for ChiLDREN terminates (current funding is until July 2014 and extension is possible), all decisions about the use of the samples will be made by the ChiLDREN Steering Committee. After funding for ChiLDREN terminates, NIDDK will set up a peer review mechanism to determine the use of the remaining samples. All patient identifiers have been removed from samples in the repositories (i.e., samples are de-identified). The study database will be transmitted to the NIDDK repository with all patient identifiers removed; e.g., dates will be converted to ages.

5. Termination or Withdrawal of Subject Participation

Subjects with biliary atresia will be followed intensively for the first year, at 18 months of age, and then annually up to 15 years of age. Other subjects with cholestasis will be followed on the same schedule; if there is complete (clinical and biochemical) resolution of their underlying liver disease off all therapy, there will be one final follow up visit within one year (preferably scheduled at the time of the next planned follow up visit or at 12 months of age, whichever is later) for data collection and to obtain blood samples.

The subject's parents or guardians may request that the subject be removed from the study at any time. In addition, the investigator may withdraw a subject from the study if he/she determines that it is in the subject's best interests.

Note: Upon request of the parents or guardians, samples and data that have been submitted to the NIDDK repository or to the data coordinating center may be destroyed unless the samples have already been used or the data have been included in reported analyses or unless the linkage between the research identifier and the subject has been destroyed.

When the study ends at a clinical site or the subject completes the study, the linkage between the samples and the subject will be destroyed. Once this linkage has been destroyed, it will no longer be possible to withdraw samples and data from the repository and the database in response to a subject request.

6. Statistical Considerations

General Design Issues:

The prospective observational database will collect data on all subjects with cholestasis who present at a ChiLDREN clinical site at ≤ 180 days of age. Since there are many

causes of cholestasis, including biliary atresia and neonatal hepatitis, the general design is that of a longitudinal cohort study, stratified by diagnosis.

Specific Aims:

The specific aims of this study are to characterize the natural history of different types of cholestatic (liver) disease by prospectively following subjects with cholestatic disease over time and to identify risk factors related to onset, to outcome and to the success of treatment(s) of each cholestatic disease, with a special emphasis on biliary atresia.

Primary Outcomes:

Disease progression defined by

1. transplantation or death,
2. increase in bilirubin or other biochemical indicators of disease progression
3. incidence of complications related to liver malfunction

Sample Size and Accrual:

It is anticipated that the 15 ChiLDREN clinical sites combined will accrue approximately 40 cases of biliary atresia annually and an equal number of cases of patients with cholestasis with a different etiology. If 75% of the eligible subjects are recruited into the observational database, there will be 30 cases per year of biliary atresia and a similar number with other diseases. The intention of the observational database is to continue to accrue subjects as long as possible—therefore, the sample size is a function of the available subjects and length of accrual. Using data from these subjects, ChiLDREN desires to estimate the incidence of the failure of treatment, factors associated with success/failure, etc.

In the table below we indicate the relationship between sample size and effect size at a fixed power. We assume that we will be comparing infants with biliary atresia to control infants when computing effect size and difference in proportions and that we are trying to identify association of covariates with outcomes for infants with biliary atresia (one sample only) in the last column. All estimates are for 80% power using a two-tailed tests at a 5% level of significance. The effect size is the expected difference between two groups divided by the standard deviation. The difference of proportions is computed for the case where one group has a proportion of 50%; the difference will be smaller when the groups have proportions nearer to zero or one.

For example, it is possible that patients with biliary atresia have a 40% rate of reovirus compared to 20% in the controls. With 85 subjects per group, or after approximately 3 years of patient accrual, there will be 80% power to observe this difference. (This differs from the table below, because we used a worst case scenario, differences from 50%, to compute the entries in the table.) Factors that are hypothesized to affect success of the portoenterostomy are age (in weeks) at the time of the portoenterostomy and the number of episodes of cholangitis after the portoenterostomy; if the association between these factors and length of time to transplant or death is 0.3 or greater, we will be able to identify this correlation with 80% power when 90 subjects with biliary atresia have been studied.

The sample size needed to test the specified effect size or difference in proportions when comparing two groups or to identify the specified correlation in a single group.

Sample size per group	Exp. number of years to attain the sample size	Effect size, if continuous	Difference in proportions (from 0.5), if discrete	Correlation (one sample only)
60	2	0.52	0.25	0.36
90	3	0.42	0.21	0.30
120	4	0.37	0.18	0.26
150	5	0.33	0.16	0.23

Data Analyses

Data cleaning. Prior to unblinding any study, the data for each variable will be examined univariately and bivariately to identify potential outliers and deviations from statistical assumptions. The goal is both to identify data values that should be queried back to the clinical site and variables that should be transformed prior to analysis.

Baseline comparisons. When groups are to be compared, the treatment groups will be compared at baseline on demographic variables and baseline values of outcome measures. Measures at baseline that differ between groups will be included as covariates in the models that are used to analyze the efficacy of the treatment.

Intent-to-treat and per protocol analyses. When groups are compared, the primary analysis will be intent to treat. Each subject will be included in the intent-to-treat analysis. All hypotheses will be tested using a two-tailed test even when the hypothesis is stated as one-sided.

Missing data. There are two types of missing data - values that are missing due to an incomplete form and visits that are missing. When a small proportion of the values (<25%) are missing in a scale, the missing values will be imputed. No values will be imputed for missing visits unless the absence of the visit in itself is meaningful, as in the evaluation of compliance with the treatment program. We will use methods of analysis, such as mixed models, that do not require complete data. When items are missing on a form and imputation is necessary, they may be multiply imputed.

Models. Longitudinal studies involve repeated evaluations of the subjects, first at screening or baseline, and then at several time points after diagnosis and treatment. When the endpoint is a time to event such as death or time to transplant, a Cox regression model will be fitted to the data. Otherwise, depending on whether the endpoint is dichotomous (improved/not improved) or continuous (bilirubin value), generalized estimating equations or random effects models will be fitted to the data. These models allow the analysis to take the within-subject correlation into account during analyses.

7. Data Management

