The treatment of idiopathic neonatal hepatitis is largely supportive, involving optimization of nutrition, prevention of vitamin deficiencies, and use of choleric agents and anti-pruritic agents²⁴. Therefore, infant formulas containing medium-chain triglyceride oil are preferred, fat soluble vitamin supplements are given, and oral ursodeoxycholic acid or cholestyramine are used to induce choleresis. In up to 20% of cases of idiopathic neonatal hepatitis, patients will show progression to cirrhosis and chronic liver failure and may require liver transplantation. In recent years, many of these patients with progressive neonatal hepatitis have been found to harbor a form of PFIC (Byler's disease), or MDR3 deficiency. Patients with PFIC types 1 and 2 may benefit from partial biliary diversion.

Outcome: If the portoenterostomy is not performed in biliary atresia, 80-90% of children will die (without liver transplantation) from biliary cirrhosis by one year of age, and 100% by two to three years of age. Successful portoenterostomy is associated with approximately a 30-40% 10-year survival at the best centers in North America and Europe^{21,25}, whereas 10-year survival following portoenterostomy in patients in Japan may exceed 65%⁴. If the portoenterostomy is not successful in establishing bile flow, survival without transplantation is similar to or worse than that of patients not undergoing surgery. Post-operative care following portoenterostomy differs in Japan from that used in the United States⁴. In Japan, intravenous bile acid treatment (which is not available in the United States) is administered for up to several months and intravenous and oral corticosteroids are routinely given for at least two months following surgery⁴. Intravenous antibiotics and herbal therapies are also commonly used following biliary atresia surgery in Asian countries. It is not clear if these differences in treatment or other factors (e.g., genetic) are responsible for the improved prognosis in Japan. The majority of surviving patients will develop complications of portal hypertension, such as esophageal variceal hemorrhage²⁶ which can generally be treated medically and

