28. Samples collected for the repository: Blood, urine, liver, gall bladder, lymph node and bile specimens. (Tissue specimens are only obtained when the tissue is removed as part of a clinical procedure, biopsy or surgery, and the tissue is in excess of that needed for diagnosis.)
30. Pathology: Findings if any biopsy was conducted: grade, cirrhosis, cholestasis, bile duct proliferation and inflammation and cells
35. Final status: completion of study, lost to follow up, or death

Post transplant follow-up data collection will be reduced to a brief interval history including major illness, complications, new diagnoses as well as growth and anthropometric parameters and measures of quality of life and functional status.

Developmental assessments:

For neurodevelopmental testing, at ages 1-2 years, the Bayley Scales of Infant Development-II or III will be performed on English speaking participants. For those subjects who are already enrolled in the PROBE study and have had the Bayley II administered at age 1; they will have the Bayley II administered at age 2. However those subjects either new to the PROBE study or those that have not had the Bayley II administered; they will have the Bayley III administered at age 1 and at age 2.

The Bayley Scales of Infant Development-III (BSID) is the most commonly reported test for preschoolers from 1 month to 42 months of age and provides information in both cognitive (the mental developmental index [MDI] and motor (the psychomotor developmental index [PDI]) domains. The BSID is well standardized and was updated in 1993 (Bayley II) and in 2005 (Bayley III), and its score is based on a mean of 100 and a standard deviation of 15. It has been proven to be a reliable and valid instrument for this age group. It has the advantage of assessing all areas of development. The Mental Development Index (MDI) assesses sensory and perceptual acuity, discrimination and response; acquisition of object constancy, memory, learning and problem solving, vocalizations communication, basis of abstract thinking, habituation, mental mapping and complex language and mathematical concept formation. The Psychomotor Skills Index (PDI) assesses degree of body control, large and fine muscle coordination, finer manipulatory skills of the hands and fingers, dynamic movement, dynamic praxis, postural imitation and stereognosis.

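### Section 6 does not say how non-biliary-atresia children who leave follow-up on recovery enter the time-to-transplant-or-death analysis; censoring them by default would overstate long-term risk in those diagnoses

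*Supplement*

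**What the plan says.** - **Exit rule.** Section 5 follows BA subjects "then annually up to 15 years of age". Other cholestatic infants share that schedule, but on complete "resolution of their underlying liver disease off all therapy, there will be one final follow up visit within one year". Section 4.1 and the schedule of evaluations (the column for complete resolution without BA) carry the same rule. The visit is preferably the next planned one or the one at 12 months of age, whichever is later.
- **Outcome and aim.** Section 6 lists "transplantation or death" first among the primary outcomes. It gives as an aim to "characterize the natural history of different types of cholestatic (liver) disease", which includes the non-BA diagnoses.
- **Method.** Section 6, Models: "When the endpoint is a time to event such as death or time to transplant, a Cox regression model will be fitted to the data". No censoring rule, competing-event method or cumulative incidence estimator is given.
- **Recording.** Section 4.4, item 35: "Final status: completion of study, lost to follow up, or death". Resolution is not a category of its own there, although it has its own visit column in the schedule.
- **Only progression figure for a non-BA diagnosis.** Section 3, Treatment: "In up to 20% of cases of idiopathic neonatal hepatitis, patients will show progression to cirrhosis and chronic liver failure".

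**The concern.** Leaving the study is tied to a good outcome, and only for the non-BA children. Follow-up that stops at exit, put into a standard Cox or Kaplan-Meier analysis, removes recovered children from the risk set. Those who remain are increasingly the progressive cases, and they then stand in for the children who left. Censoring of this kind is informative for anyone who reads the result as the risk carried by an infant with that diagnosis.

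The natural-history aim is most exposed: the proportion of each non-BA diagnosis that reaches transplant or death by a given age. About half the cohort is involved, since Section 6 expects 30 BA cases a year and a similar number with other diseases. Any overall comparison of BA with other diagnoses on this endpoint would be affected too.

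**Working it through.** The documents state no transplant or death risk, resolution rate or resolution time for non-BA subjects, so there is no planned figure to reproduce. The check compares two quantities under stated assumptions: the true cumulative risk, with recovered children counted as event-free, and the estimate obtained when they are censored at exit. All cases assume no transplant or death after resolution.

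**Inputs**
- Progressive share p = 20%. This is Section 3's upper figure for idiopathic neonatal hepatitis; applying it to other diagnoses is an assumption. p = 40% is tried as well.
- Event hazard h among progressive cases: 0.05 to 0.3 per year (assumed).
- Median time to resolution m among the rest: 0.5 to 2 years (assumed). Exit is at the later of resolution + 0.5 year and 1 year, approximating Section 5.
- BA hazard: Section 3 gives 30–40% 10-year survival after successful portoenterostomy. Taking 35%, −ln(0.35)/10 = 0.105 per year (assumed to serve as the event rate).

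**1. Staggered resolution.** True risk is p(1 − e^(−ht)). Let G(t) be the share of recovering children still in follow-up: G = 1 before 1 year, then e^(−λ(t − 0.5)) with λ = ln 2/m. The hazard in the censored risk set is h·p·e^(−ht) / [p·e^(−ht) + (1 − p)·G(t)], and the censored risk is 1 − exp(−its integral).

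Example with h = 0.1 and m = 1, at 5 years. Progressive cases still event-free: 0.2 × e^(−0.5) = 0.121. Recovering children still in follow-up: 0.8 × 2^(−4.5) = 0.035. Progressive cases form 0.121/0.157 = 77% of the censored risk set, against 0.121/(0.121 + 0.8) = 13% of all event-free children.

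| h per year | m (years) | 2-year true / censored | 10-year true / censored |
|---|---|---|---|
| 0.05 | 0.5 | 1.9% / 3.3% | 7.9% / 34% |
| 0.05 | 2 | 1.9% / 2.2% | 7.9% / 22% |
| 0.1 | 1 | 3.6% / 4.8% | 12.6% / 50% |
| 0.3 | 0.5 | 9.0% / 15.7% | 19.0% / 91% |
| 0.3 | 2 | 9.0% / 10.3% | 19.0% / 47% |

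Over this range the 10-year risk is 8–19% true and 22–91% censored. With p = 40% it is 16–38% true and 29–93% censored.

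**2. Constant competing hazards.** Total hazard L, of which a fraction p is events: true risk p(1 − e^(−Lt)), censored estimate 1 − e^(−pLt). With p = 20%:
- L = 0.35: 2 years 10.1% / 13.1%; 10 years 19.4% / 50%.
- L = 1.4: 2 years 18.8% / 42.9%; 10 years 20.0% / 94%.

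**3. Sharp exit.** All of the 80% leave at exactly 12 months. Censored survival at 10 years is [1 − 0.2(1 − e^(−h))] × e^(−9h), with h = ln 2/median event time.
- Median 1 year: 0.900 × 0.00195 gives a risk of 99.8%; true 20%.
- Median 3 years: 0.959 × 0.125 gives 88%; true 18%.
- Median 5 years: 0.974 × 0.287 gives 72%; true 15%.

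Replacing e^(−9h) by e^(−h) gives the 2-year figures: 55%, 24% and 15% censored against 15%, 7.4% and 4.8% true.

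**4. Contrast with BA.** Simulating case 1 against the BA hazard above, the BA versus non-BA Cox hazard ratio is 0.7–4.6 with exit censored and 6.1–14.6 with recovered children kept event-free. Hazards are not proportional here, so these are averages over follow-up.

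**5. Limit.** If hardly anyone resolves, G(t) stays near 1, the risk set is nearly the whole diagnosis group, and the two estimates agree.

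**The case against.** A reader might infer four stronger things that the documents do not support.

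- **That the plan censors these children.** It does not say so; it gives no rule. Only the protocol is shown, and censoring rules are often left to an analysis plan. That stands as a limit on the wording. It does not remove the point, because this protocol states both the outcome-dependent exit and the sole time-to-event method, and together they lead to the problem unless something is added.
- **That a BA versus non-BA hazard ratio for transplant or death is planned.** It is not. The cohort is stratified by diagnosis, the BA-versus-control sample sizes concern means and proportions, and the worked example for time to transplant or death is within BA. The hazard ratios above show what such a contrast would do, not a planned result.
- **That Cox is the wrong model.** With resolution censored it still gives a valid cause-specific hazard among unresolved children. The error lies in reading that as cumulative risk or as the overall difference between diagnoses.
- **That the overstatement is gross everywhere.** The 20% figure belongs to one diagnosis, and not progressing to cirrhosis is not the same as complete resolution off therapy. The sharp-exit case is an extreme.

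Nor does the final-status item lose essential information. A non-BA child who completes well before age 15 can be identified from the diagnosis, the resolution visit, and the laboratory and medication records. An explicit category is a convenience.

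**Conclusion.** The point holds as a missing rule with a predictable consequence. If recovered non-BA children are censored at exit, cumulative transplant or death risk in those diagnoses is biased upward, and any overall contrast with BA is biased toward or past 1. The direction is the same in every case tried; the size is not known from the documents. With a 20% progressive share the 10-year overstatement is about 2.5 to 5 times (22–91% against 8–19% under staggered resolution). At 2 years it is about 1.1 to 2.3 times in the staggered and constant-hazard cases, and more than 3 times only if everyone who recovers leaves at exactly 12 months. It is slight for diagnoses that seldom resolve. BA-only Cox analyses, the plan's main emphasis, are untouched. The figures rest on assumed resolution and event rates and on no transplant or death after resolution. This deserves a change in Section 6; it does not undermine the study.

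**What to change.** In Section 6:
1. Define complete resolution off therapy as a competing event for transplant or death in non-BA subjects, and report Aalen-Johansen cumulative incidence by diagnosis.
2. Label any Cox result with resolution censored as a cause-specific hazard among unresolved children, not as overall risk.
3. Add a sensitivity analysis that keeps recovered children event-free to the earlier of age 15 and the data cut-off.
4. State the assumption that no transplant or death follows resolution.

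In Section 4.4, record complete resolution and its date explicitly at the final visit, for example as its own category in item 35.

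The cost is a few sentences, one form entry and a little more analysis work, with no extra visits. The downside is the assumption in step 4. The planned follow-up cannot test it, and checking later would be harder because Section 5 has the link between samples and subject destroyed once a subject completes the study.

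### The 80% power for a 0.3 association with time to transplant or death in 90 subjects comes from a complete-data correlation formula, while the planned Cox analysis depends on the number of events, which the plan does not state

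*Supplement*

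**What the plan says.** The power statement is in Section 6, under Sample Size and Accrual. It names two factors thought to affect the success of portoenterostomy: age in weeks at the operation, and the number of cholangitis episodes after it. The claim concerns an association of at least 0.3 between such a factor and the time until either event, and reads: "we will be able to identify this correlation with 80% power when 90 subjects with biliary atresia have been studied". The general conditions are "All estimates are for 80% power using a two-tailed tests at a 5% level of significance".

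The accompanying table gives a one-sample correlation of 0.36, 0.30, 0.26 and 0.23 for 60, 90, 120 and 150 subjects. With 75% recruitment the section expects that "there will be 30 cases per year of biliary atresia", so the table puts 90 subjects at 3 years.

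Transplantation or death is the first component of the primary outcome. Under Models, the plan says: "When the endpoint is a time to event such as death or time to transplant, a Cox regression model will be fitted to the data". Section 6 gives no expected number of events, event fraction, hazard ratio, censoring allowance or minimum follow-up to go with the 80%.

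**The concern.** A correlation calculation assumes that the outcome is known for every subject. Time to transplant or death is not: a child alive with the native liver at the analysis contributes a censored time. In a Cox model the information about a covariate comes from the events, so 90 enrolled subjects carry the stated power only if nearly all have had the event, or if the effect is larger on the hazard scale than 0.3 suggests.

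The background section rules out complete observation. It says "Successful portoenterostomy is associated with approximately a 30-40% 10-year survival" at the best North American and European centres, and that 70 to 80% of patients are transplanted over two decades. Some children will therefore never have the event while followed.

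This is the only power figure that Section 6 attaches to a named primary outcome, and it serves the aim of finding risk factors for outcome and treatment success. A null result in 90 subjects could be read as excluding a 0.3 association when the chance of detecting one was well below 80%.

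There is a second, separate issue. Both factors are defined only for infants who had a portoenterostomy, while the 90 counts all biliary atresia. Section 3 notes that many surgeons do not operate on infants who present beyond 3 to 4 months.

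**Working it through.** **1. Reproducing the plan's figure.** With two-sided 5% and 80% power, the detectable correlation under the simple normal form is r = (1.960 + 0.842)/sqrt(N).

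| N | Computed r | Table |
|---|---|---|
| 60 | 0.362 | 0.36 |
| 90 | 0.295 | 0.30 |
| 120 | 0.256 | 0.26 |
| 150 | 0.229 | 0.23 |

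All four entries match after rounding. Power at N = 90 and r = 0.30 is Phi(0.30 × sqrt(90) − 1.960) = 81.2%. Fisher's z gives 82.3%, but its detectable values (0.355, 0.292, 0.253, 0.227) do not round to the printed 0.30 and 0.26. The formula has no event term.

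**2. Cox power.** For a baseline covariate scaled to SD 1, power = Phi(sqrt(d) × b − 1.960), where d is the number of events and b the absolute log hazard ratio per SD. Events needed for 80% power are 2.802²/b² = 7.85/b².

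The plan does not say how 0.3 maps to b. Three readings, the last two assuming exponential event times:
- b = 0.30, the number taken directly: 87 events.
- b = 0.333, a correlation of 0.30 with time, from b/sqrt(2exp(b²) − 1) = 0.30: 71 events.
- b = 0.403, a correlation of 0.30 with log time, from b/sqrt(b² + π²/6) = 0.30: 48 events.

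| Events of 90 | b = 0.30 | b = 0.333 | b = 0.403 |
|---|---|---|---|
| 27 | 34% | 41% | 55% |
| 45 | 52% | 61% | 77% |
| 63 | 66% | 75% | 89% |
| 72 | 72% | 81% | 93% |
| 90 | 81% | 89% | 97% |

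Simulated Cox fits (N = 90, uniform censoring, about 45 events) gave 49%, 58% and 74%, slightly below the formula.

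**3. Expected events.** These inputs are assumptions built from Section 3:
- Bile drainage in 40 to 80% of subjects.
- Without drainage, 80 to 90% have the event by one year. Section 3 gives this for unoperated children and calls failed surgery similar or worse.
- After success, 30 to 40% 10-year survival, read as survival without transplant.
- Constant hazards counted from enrolment, and uniform entry over 3 years.

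The event fraction with follow-up uniform on 0 to 3 years is 1 − (1 − exp(−3h))/(3h).
- Low end (80% drainage): h = −ln 0.2 = 1.609 per year for failures, fraction 0.794. For successes h = −ln 0.4/10 = 0.092, fraction 0.126. Events = 90 × (0.2 × 0.794 + 0.8 × 0.126) = 23.
- High end (40% drainage): h = −ln 0.1 = 2.303, fraction 0.855. For successes h = −ln 0.3/10 = 0.120, fraction 0.161. Events = 90 × (0.6 × 0.855 + 0.4 × 0.161) = 52.

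With 10 years of follow-up for each subject, essentially all failures have had the event. Events = 90 × (0.2 + 0.8 × 0.6) = 61 at the low end and 90 × (0.6 + 0.4 × 0.7) = 79 at the high end.

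| Analysis time | Events | b = 0.30 | b = 0.333 | b = 0.403 |
|---|---|---|---|---|
| 90th subject enrolled | 23–52 | 30–58% | 36–67% | 50–83% |
| Two years later | 37–66 | 45–68% | 53–77% | 69–91% |
| 10 years each | 61–79 | 65–76% | 74–84% | 88–95% |

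**4. Detectable hazard ratio per SD at 80% power**, exp(2.802/sqrt(d)): 1.75 at 25 events, 1.49 at 50, and 1.34 if all 90 had the event.

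**The case against.** The sentence names no analysis time. The table's column counts years to reach a sample size, and only the reovirus example, a comparison of infection rates between groups, mentions about 3 years of accrual. Biliary atresia subjects are followed up to 15 years of age, accrual is open-ended, and no decision depends on 90 subjects. A reader might infer that the plan promises 80% power at year 3. It does not, and the year-3 rows above are one scenario.

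A reader might also infer that censoring fixes power at some range such as 40 to 80%, or that 80% cannot be reached. The documents support neither. With 10 years of follow-up the log-time reading gives 88 to 95%, and even at year 3 its upper end is 83%. Before any censoring, that reading gives 97%, so the plan's formula is not always optimistic.

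The event model can be challenged too. Section 3 gives only 10 to 20% drainage after 12 weeks, and infants may present up to 180 days. Including that group would raise the event count. In the other direction, the calculation uses all 90 subjects although some will not be operated on, and the documents do not give that share.

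These points limit how precisely the shortfall can be stated. They leave the defect in place: the 80% comes from a formula without events, for an endpoint whose planned analysis depends on them. Taking studied to mean followed to the event does not rescue it, because the plan does not say so and some children would never qualify.

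**Conclusion.** The concern holds in conditional form. The correlation column is arithmetically right for fully observed outcomes, but applying it to time to transplant or death is unsupported.

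Under the assumptions listed above, power for a 0.3 association in 90 subjects is about 30 to 83% if analysed when the 90th enrols, and about 65 to 95% with some 10 years of follow-up each. These ranges reflect the unknown drainage share, analysis time and mapping of 0.3 to a log hazard ratio per SD (0.30 to 0.40). They are not bounds fixed by the documents. If 0.3 is itself the log hazard ratio per SD, 80% needs about 87 events in 90 subjects, and even 10 years of follow-up gives only 65 to 76%. Restricting to operated infants lowers the usable number further, by an amount the documents do not allow one to compute.

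The statement should be corrected. It does not set the study's size and does not put the cohort itself in doubt.

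**What to change.** - Limit the correlation column to fully observed outcomes, and say so in its heading or a note.
- Replace the sentence with an events-based one. For a baseline factor such as age at portoenterostomy, give events needed for 80% power as 7.85/(ln HR per SD)². State the expected events among operated subjects at each intended analysis time, with the assumptions behind them, and the detectable hazard ratio per SD that follows (for example 1.75 at 25 events, 1.49 at 50, 1.34 at 90).
- State when the analysis will be done, or the event count that triggers it.
- Do not use that formula unmodified for the number of cholangitis episodes. The count builds up during follow-up, so it should enter the Cox model as a time-dependent covariate, with its own power statement or none.

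The cost is an edit to one sentence and one table column. The stated figure will probably look less favourable. No more patients or visits are needed.
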